2.3. Posttreatment Week 24 Analysis (Final Analysis)

After all subjects have completed the study, outstanding data queries have been resolved, and the database has been cleaned and finalized, the final analysis of the data will be performed.

3. GENERAL CONSIDERATIONS FOR DATA ANALYSES

Analysis results will be presented using descriptive statistics. For categorical variables, the number and percentage of subjects in each category will be presented; for continuous variables, the number of subjects (n), mean, standard deviation (SD) or standard error (SE), median, first quartile (Q1), third quartile (Q3), minimum, and maximum will be presented.

By-subject listings will be presented for all subjects in the Safety Analysis Set and sorted by subject ID number, visit date, and time (if applicable). Data collected on log forms, such as AEs, will be presented in chronological order within the subject. The treatment group to which subjects were initially assigned will be used in the listings. Age, sex at birth, race, and ethnicity will be included in the listings, as space permits.

3.1. Analysis Sets

Analysis sets define the subjects to be included in an analysis. Analysis sets and their definitions are provided in this section. The number of subjects eligible for each analysis set will be provided. Subjects who were excluded from each analysis set will be summarized or provided in a by-subject listing with reasons for exclusion.

3.1.1. All Enrolled Analysis Set

All Enrolled Analysis Set includes all subjects who received a study subject identification number in the study after screening.

3.1.2. Full Analysis Set

The Full Analysis Set (FAS) includes all enrolled subjects who took at least 1 dose of study drug in this study, which is SOF/VEL FDC. This is the primary analysis set for efficacy analyses.

3.1.3. Safety Analysis Set

The Safety Analysis Set includes all subjects who took at least 1 dose of study drug. This is the primary analysis set for safety analyses. Treatment-emergent data will be analyzed and defined as data collected from the first dose of the study drug through the date of last dose of the study drug plus 30 days.

3.2. Subject Grouping

For analyses based on the All Enrolled Analysis Set, FAS, or demographic and baseline characteristics tables, subjects will be grouped according to the HCV genotype (GT1 with GT1 broken down as GT1a and GT1b; non-GT1 with non-GT1 broken down as GT2, GT2a/2c and GT2b).

3.3. Examination of Subject Subgroups

Subject subsets within each genotype will also be explored by presumed prognostic baseline characteristics for the primary efficacy endpoint, SVR12. The presumed prognostic baseline characteristics include the following:

- age (< 65 years, \ge 65 years)
- sex (male, female)
- baseline body mass index (BMI) ($< 25 \text{ kg/m}^2$, $\ge 25 \text{ kg/m}^2$)
- IL28B (CC, non-CC; with non-CC further broken down to CT, TT)
- baseline HCV RNA (< 800,000 IU/mL, ≥ 800,000 IU/mL)
- baseline alanine aminotransferase (ALT) ($\leq 1.5 \times$ upper limit of normal (ULN), $> 1.5 \times$ ULN)
- prior HCV treatment experience (treatment naive, treatment experienced)
- prior HCV treatment (pegylated interferon [Peg-IFN], Other) for treatment experienced subjects
- prior HCV treatment response (non-responder, relapse/breakthrough, early treatment discontinuation, met a virologic stopping rule, unknown) for treatment experienced subjects
- study treatment status (completed study treatment, discontinued study treatment)
- adherence to study regimen (< 80%, > 80%)

3.4. Multiple Comparisons

No multiplicity adjustment will be made for testing because only one test will be performed.

3.5. Missing Data and Outliers

3.5.1. Missing Data

In general, missing data will not be imputed unless methods for handling missing data are specified. Exceptions are presented in this document.

For missing last dosing date of study drug, imputation rules are described in Section 3.7.1. The handling of missing or incomplete dates for AE onset is described in Section 7.1.5.2, and for prior and concomitant medications in Section 7.4.

For analyses of categorical HCV RNA data, missing posttreatment HCV RNA data will have the missing data imputed. Missing on-treatment HCV RNA will have missing data imputed up to the time of the last dose (for on-treatment displays). If the study day associated with the last dosing date of the study drug is greater than or equal to the lower bound of a visit window, and the value at the visit is missing, then the value will be imputed. If the study day associated with the last dosing date is less than the lower bound of a visit window, then the on-treatment value at that visit will remain missing.

If an HCV RNA data point is missing and is preceded and followed in time by values that are "< lower limit of quantification (LLOQ) target not detected (TND)," then the missing data point will be set to "< LLOQ TND." If a data point is missing and preceded and followed by values that are "< LLOQ detected," or preceded by "< LLOQ detected" and followed by "< LLOQ TND," or preceded by "< LLOQ TND" and followed by "< LLOQ detected," then the missing value will be set to "< LLOQ detected." In these situations, the data point will be termed a bracketed success; otherwise, the data point will be termed a bracketed failure (ie, \geq LLOQ detected). If a data point is missing and is not bracketed, the missing data point will also be termed a failure (ie, \geq LLOQ detected) except for SVR24, which will be imputed according to SVR12 status. Success for SVR12 who have no further HCV RNA measurements collected will be counted as a success for SVR24 due to the high correlation between these 2 endpoints.

For the analyses of continuous HCV RNA efficacy data, when and only when a missing HCV RNA value is imputed as < LLOQ TND or < LLOQ detected according to the imputation rule described above, the corresponding continuous value will be imputed to LLOQ – 1 IU/mL. No other imputation will be performed for continuous HCV RNA data.

3.5.2. Outliers

Outliers will be identified during the data management and data analysis process, but no sensitivity analyses will be conducted. All data will be included in the data analysis.

3.6. Data Handling Conventions and Transformations

By-subject listings will be presented for all subjects in the Safety Analysis Set and sorted by subject ID number, visit date, and time (if applicable) unless otherwise specified. Data collected on log forms, such as AEs, will be presented in chronological order within subject.

Age (in years) on the date of the first dose of study drug and sex at birth will be used for analyses and presentation in listings.

If a subject was never dosed with study drug, then the date the informed consent was signed will be used instead of the first dose date of study drug. For some countries, only birth year is collected on the CRF. In those cases, "01 January" will be used for the unknown birth day and month for the purpose of age calculation, unless age is captured on the CRF.

Non-PK data that are continuous in nature but less than the lower limit of quantitation (LOQ) or above the upper limit of quantitation will be imputed as follows:

- A value that is 1 unit less than the limit of quantitation will be used for calculation of descriptive statistics if the datum is reported in the form of "< x" (where x is considered the LOQ). For example, if the values are reported as < 50 and < 5.0, values of 49 and 4.9, respectively, will be used for calculation of summary statistics. An exception for this rule is any value reported < 1. For the values reported as < 1 or < 0.1, a value of 0.9 or 0.09, respectively, will be used for calculation of summary statistics.
- A value that is 1 unit above the LOQ will be used for calculation of descriptive statistics if the datum is reported in the form of "> x" (where x is considered the LOQ). Values with decimal points will follow the same logic as above.
- The LOQ will be used for calculation of descriptive statistics if the datum is reported in the form of " \leq x" or " \geq x" (where x is considered the LOQ).

The COBAS® AmpliPrep/COBAS® TaqMan® HCV Quantitative Test, v2.0 was used to determine HCV RNA results in this study. The LLOQ of the assay is 15 IU/mL.

When the calculated HCV RNA value is within the linear range of the assay, then the result will be report as the "<< numeric value>> IU/mL." This result will be referred to in this document as the numeric result or as " \geq LLOQ detected" for categorical result.

When HCV RNA is not detected, the result is reported as "No HCV RNA detected" or "target not detected". This result will be referred to in this document as "< LLOQ target not detected" or "< LLOQ TND."

When the HCV RNA IU/mL is less than LLOQ of the assay, the result is reported as "< 15 IU/mL HCV RNA detected." This result will be referred to in this document as "< LLOQ detected."

The overall category of HCV RNA < LLOQ includes "< LLOQ TND" and "< LLOQ detected."

For numerical HCV RNA data, values below LLOQ will be set to the LLOQ – 1 IU/mL (ie, 14 HCV RNA IU/mL). HCV RNA values returned as "No HCV RNA detected" will also be set to 14 IU/mL.

For selected analyses, HCV RNA data (IU/mL) will be transformed to the logarithmic (base 10) scale (log₁₀ IU/mL).

3.7. Visit Windows

3.7.1. Definition of Study Day

Study day is the day relative to the date of the first dose of study drug. Study Day 1 will be defined as the day of first dose of study drug administration.

Study day will be calculated from the date of first dose of study drug administration and derived as follows:

- For postdose study days: Assessment Date First Dosing Date + 1
- For days prior to the first dose: Assessment Date First Dosing Date

The last dose date for the study drug will be the end date on study drug administration eCRF for the record where the "subject permanently discontinued" flag is 'Yes'.

If there are subjects for whom the date of last study drug is unknown due to the reason that the subject was lost to follow-up and not able to be contacted, the date of last dose will be estimated using the maximum of nonmissing study drug start or stop dates, visit dates, and laboratory collection dates (posttreatment visits and unscheduled visits are not included).

3.7.2. Analysis Visit Windows

Subject visits might not occur on protocol-specified days. Therefore, for the purpose of analysis, observations will be assigned to analysis windows.

In general, the baseline value will be the last nonmissing value on or prior to the first dose date of study drug.

HCV RNA, vital signs, and safety laboratory data collected up to the last dose date + 3 days are considered to be on-treatment data and HCV RNA, vital signs, and safety laboratory data collected after the last dose date + 3 days are considered posttreatment data. The analysis windows for on-treatment HCV RNA, vital signs and safety laboratory data are provided in Table 1.

Table 1. Analysis Visit Windows for On-treatment HCV RNA, Vital Signs and Safety Laboratory Data

	HCV RNA	and Safety Labo	oratory Data	Vital Signs Data			
Nominal Visit	Nominal FU Day	Lower Limit	Upper Limit	Nominal FU Day	Lower Limit	Upper Limit	
Baseline	1	(none)	1	1	(none)	1	
Week 1	N/A	N/A	N/A	7	2	11	
Week 2	14	2	21	14	12	21	
Week 4	28	22	42	28	22	42	
Week 8	56	43	70	56	43	70	
Week 12	84	71	≥ 85	84	71	≥ 85	

HCV RNA, vital sign, and safety laboratory data collected after the last dose date + 3 days will be assigned to the posttreatment follow-up (FU) visit. Visit windows will be calculated from the last dose date (ie FU Day = collection date minus the last dose date) as shown in Table 2.

Table 2. Analysis Visit Windows for Posttreatment HCV RNA, Vital Signs and Safety Laboratory Data

		HCV RNA		Vital Signs and Safety Laboratory Dat			
Nominal FU ^a Visit	Nominal FU Day	Lower Limit	Upper Limit	Nominal FU Day	Lower Limit	Upper Limit	
FU-4	28	21	69	28	4	30	
FU-12	84	70	146	NA	NA	NA	
FU-24	168	147	210	NA	NA	NA	

a FU-x visit = posttreatment Week-x follow-up visit.

ECG data collected up to the last dose date + 3 days are considered to be on-treatment data. Qualitative assessments of whether the ECG is normal or abnormal will be assessed for on-treatment data based on the visit windows shown in Table 3.

Table 3. Analysis Visit Windows for On-treatment ECG Data

Nominal Visit	Nominal Day	Lower Limit	Upper Limit
Baseline	1	(none)	1
Week 12	84	2	(none)

Note: ECGs are to be collected at screening, baseline, Week 1, and Week 12 or Early Termination. For purposes of analysis, baseline value will be the last available value prior to the first dose of study drug and end of treatment value will be the last available value on or prior to the last dose date + 3 days.

3.7.3. Selection of Data in the Event of Multiple Records in an Analysis Visit Window

Depending on the statistical analysis method, single values may be required for each analysis window. For example, change from baseline by visit usually requires a single value, whereas a time-to-event analysis would not require 1 value per analysis window.

If multiple valid, nonmissing measurements exist in an analysis window, records will be chosen based on the following rules if a single value is needed:

• For baseline, the last available record on or prior to the date of the first dose of study drug will be selected. If there are multiple records with the same time or no time recorded on the same day, the average (arithmetic mean) will be used for the baseline value. If multiple ECG measurements occur on the same day prior to first dose of any study drug, the average will be used as baseline for continuous data, regardless of the timing of these multiple ECG measurements.

b Days are calculated based on last dose date.

• For postbaseline values:

- The record closest to the nominal day for that visit will be selected except for HCV RNA
 posttreatment follow-up visits, for which the latest record in the analysis window will be
 selected.
- If there are 2 records that are equidistant from the nominal day, the later record will be selected.
- If there is more than 1 record on the selected day, the average will be taken, unless otherwise specified.
- If multiple valid nonmissing categorical observations exist in a window, records will be selected as follows:
 - For baseline, the last available record on or prior to the date of the first dose of study drug will be selected. If there are multiple records with the same time or no time recorded on the same day, the value with the lowest severity will be selected (eg, normal will be selected over abnormal). If multiple ECG measurements occur on the same day prior to the first dose of any study drug, the value with the lowest severity will be selected regardless of the timing of these multiple ECG measurements.
 - For postbaseline visits, follow the same rules described above for postbaseline numeric observations, except that if there are multiple records on the same day, the most conservative value will be selected (eg, abnormal will be selected over normal).

4. SUBJECT DISPOSITION

4.1. Subject Enrollment and Disposition

A summary of subject enrollment will be provided for each investigator. The summary will present the number and percentage of subjects in the Safety Analysis Set. For each column, the denominator for the percentage calculation will be the total number of subjects analyzed for that column.

A summary of subject disposition will be provided by HCV genotype (GT1, GT1 broken down [1a, 1b], GT2, GT2 broken down [GT2a/2c, GT2b]) and overall. This summary will present the number of subjects screened, the number of subjects enrolled, the number of subjects enrolled but never treated, and the number and percentage of subjects in each of the categories listed below

- In Safety Analysis Set
- In FAS
- Completed study treatment
- Did not complete study treatment with reasons for premature discontinuation of study treatment
- Completed study follow-up
- Did not complete the study follow-up with reasons for premature discontinuation of study follow-up

Among subjects who completed study treatment and who discontinued study treatment, the number and percentage of subjects will be summarized for:

- Who had no HCV posttreatment Week 4 assessment and thereafter (No HCV FU-4 Assessment and thereafter)
- Who had HCV posttreatment Week 4 assessment but no HCV posttreatment Week 12 and thereafter (With HCV FU-4 but No FU-12 and thereafter)

If a subject did not have any HCV RNA assessment \geq 21 days after the last dose of any study drug (ie, lower bound of FU-4 visit for HCV RNA data), the subject is categorized as having "No HCV FU-4 and thereafter." If a subject had the HCV FU-4 assessment but did not have any HCV RNA assessment \geq 70 days after the last dose of any study drug (ie, lower bound of FU-12 visit for HCV RNA data), the subject is categorized as having "With HCV FU-4 but No FU-12 and thereafter."

In addition, the total number of subjects who were enrolled, and the number of subjects in each of the disposition categories listed above will be depicted by a flowchart.

The following by-subject listings will be provided by subject identification (ID) number in ascending order to support the above summary tables:

- Disposition for subjects who complete study treatment and study follow up
- Disposition for subjects who did not complete study treatment and/or study follow up with reasons for premature discontinuation of study treatment and/or study
- Lot number and kit ID (if applicable)

4.2. Extent of Exposure

Extent of exposure to study drug will be examined by assessing the total duration of study drug exposure and the level of adherence to the study drug regimen specified in the protocol.

4.2.1. **Duration of Exposure to Study Drug**

Total duration of exposure to study drug will be defined as last dose date minus first dose date plus 1, regardless of any temporary interruptions in study drug administration, and will be expressed in weeks using up to 1 decimal place (eg, 4.5 weeks).

The total duration of exposure to study drug will be summarized using descriptive statistics (n, mean, SD, median, Q1, Q3, minimum, and maximum) and using the number of subjects (ie, cumulative counts) and percentage of subjects exposed through the following time periods: baseline (Day 1), Week 1 (Day 7), Week 2 (Day 14), Week 4 (Day 28), Week 6 (Day 42), Week 8 (Day 56), Week 10 (Day 70), and Week 12 (Day 84). A 3-day window is applied to the last planned on-treatment visit to match with the protocol-specified visit window, ie, the number of subjects exposed through Week 12 will be calculated as the number of subjects who were exposed to study drug for at least 81 days. Summaries will be provided for the Safety Analysis Set.

4.2.2. Adherence to Study Drug

The presumed total number of tablets administered to a subject will be determined by the data collected on the drug accountability CRF using the following formula:

Total Number of Doses Administered =
$$\left(\sum \text{No. of Tablets Dispensed}\right) - \left(\sum \text{No. of Tablets Returned}\right)$$

The level of adherence to the study drug regimen will be assessed based on the total amount of study drug administered relative to the total amount of study drug prescribed at baseline.

The level of adherence will be expressed in percentage using the following formula:

Level of Adherence (%) =
$$\left(\frac{\text{Total Amount of Study Drug Administered}}{\text{Total Amount of Study Drug Prescribed at baseline}}\right) \times 100$$

Note: If calculated adherence is greater than 100%, the result will be set to 100%.

In this study, the total amount of SOF/VEL (400/100 mg) prescribed for 12 weeks would require 84 tablets for each subject.

Subjects who prematurely discontinue study drug for lack of efficacy (ie, virologic failure) will have the total amount of study drug prescribed calculated up to the first date when virologic failure criteria were met. For virologic failure confirmed by 2 consecutive measurements, the date of the first measurement will be used. If study drug bottles are dispensed on or after the subject first met virologic failure criteria, these bottles will not be included in the calculation of adherence. If a bottle is dispensed and the bottle is returned empty, then the number of tablets returned will be entered as zero. If a bottle is dispensed but not returned (missing), the number of tablets taken from that bottle will be counted as zero.

Descriptive statistics for the level of adherence (n, mean, SD, median, Q1, Q3, minimum, and maximum) with the number and percentage of subjects belonging to adherence categories (eg, [< 80%, ≥ 80 to < 90%, $\ge 90\%$]) will be provided for the Safety Analysis Set. Categorical displays also will be provided for the number of subjects who are at least 80% adherent to their drug regimen (ie, adherence is $\ge 80\%$ for the study drugs).

No inferential statistics will be provided for duration of exposure and adherence to study drug.

A separate by-subject listing of study drug administration and drug accountability will be provided by subject ID number (in ascending order) and visit (in chronological order).

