3.4.2. Virologic Response-Based Treatment Stopping Criteria

The following on-treatment Virologic Response-based Treatment Stopping Criteria will be utilized:

- Confirmed HCV RNA ≥ LLOQ after 2 consecutive HCV RNA < LLOQ
- Confirmed > 1 log₁₀ increase in HCV RNA from nadir
- HCV RNA \geq LLOQ through 8 weeks of treatment

Confirmation, when required, should be performed as soon as possible and must occur no later than 2 weeks after an initial observation indicating virologic failure during the on-treatment phase.

Subjects who terminate study drug early due to virologic failure as defined above will complete the Early Termination (ET) visit and all posttreatment visits.

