6.2. Treatment Assessments (± 3 days)

On-treatment visits will be performed at the end of Weeks 1, 2, 4, 8, and 12 for all subjects.

Study drug will be reconciled at every post-Day 1 visit by the investigator in order to monitor the subject's adherence with the study drug.

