6.2.3. Weeks 4 and 8 (\pm 3 days)

The following procedures/assessments are to be completed at the end of Weeks 4 and 8:

- Obtain vital signs (refer to Section 6.7.4)
- Assessment of AEs and concomitant medications
- Assess adherence with study drug dosing regimen including pill count
- Dispense study drug as directed by the IWRS (Week 4 only)
- Obtain blood samples for tests:
 - Hematology
 - Chemistry
 - HCV RNA
 - HCV resistance samples
 - HBV DNA Sample
- Obtain urine sample for:
 - Pregnancy test for females of childbearing potential only

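### For subjects who stop drug for virologic failure, the SAP's adherence ratio ends the denominator at first failure but not the numerator, so adherence can be overstated

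*SAP*

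**What the plan says.** SAP 4.2.2 defines adherence as the amount administered divided by the amount prescribed. For the numerator, "The presumed total number of tablets administered to a subject will be determined by the data collected on the drug accountability CRF", as tablets dispensed minus tablets returned. The default denominator is 84 tablets.

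Subjects who stop drug early for lack of efficacy have a different denominator: the prescribed amount is "calculated up to the first date when virologic failure criteria were met". Where failure is confirmed by two consecutive measurements, "the date of the first measurement will be used". The only matching change to the numerator concerns bottles dispensed on or after the date of first failure: "these bottles will not be included in the calculation of adherence". The cap reads "If calculated adherence is greater than 100%, the result will be set to 100", in percent.

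Three parts of the Protocol bear on this:
- Section 3.4.2 says that confirmation "must occur no later than 2 weeks after an initial observation indicating virologic failure during the on-treatment phase".
- Sections 6.1.2 and 6.2.3 and Appendix 2 schedule dispensing at Day 1 and Week 4, and none at Week 8.
- Section 6.2 says "Study drug will be reconciled at every post-Day 1 visit by the investigator", to monitor adherence.

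SAP 3.3 makes adherence, cut at 80%, a subgroup for SVR12. SAP 6.1.4 plans exact confidence intervals and a forest plot for the subgroups.

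**The concern.** A ratio of tablets taken to tablets due needs the same end date above and below the line. Here the denominator stops at the first failing sample. The numerator stops only for bottles not yet dispensed. Tablets taken from earlier bottles while confirmation is awaited add to intake but not to what was due.

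Only subjects who stop for virologic failure get the shortened denominator; completers and relapsers keep 84. The possible overstatement therefore falls on the subjects for whom a reader most wants to know whether the drug was taken. In a 36-subject trial the low-adherence stratum may be very small, so one misplaced failure could change what that row shows.

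**Working it through.** **The plan's own figure.** 12 weeks × 7 days × 1 tablet = 84 tablets, as SAP 4.2.2 states. This equals three bottles of 28 (Protocol 5.2.2).

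**Which visit matters.** HCV RNA is scheduled at Weeks 2, 4, 8 and 12. The breakthrough stopping rule in Protocol 3.4.2 needs two earlier values below LLOQ, so on scheduled visits it is first met at Week 8. The nonresponse rule is also met at Week 8. All scheduled dispensing has happened by then, so the bottle exclusion removes nothing, however bottles were split between Day 1 and Week 4. For a failure first seen at Week 4, bottles dispensed that day are excluded and only tablets left from Day 1 can leak into the numerator. A failure at Week 12 leaves little or no treatment to cut short.

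**Inputs for a Week 8 failure.** Denominator: 56 tablets (Day 56, one per day). Dosing days after the failing sample: d. I take d = 7 and d = 14; 14 is the longest confirmation interval in Protocol 3.4.2. The documents do not give the actual time to last dose, so d is an assumption.

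**Same adherence a before and after failure.** Reported value = (56a + d·a)/56 = a(56 + d)/56, capped at 100%.

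| d | Multiplier | Reported if a = 75% | Smallest a reported as 80% or more |
|---|---|---|---|
| 7 | 63/56 = 1.125 | 84.4% | 0.80/1.125 = 71.1% |
| 14 | 70/56 = 1.25 | 93.75% | 0.80/1.25 = 64.0% |

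In this case nobody below 80% reaches 100% within 14 days: 79% × 1.25 = 98.75%.

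**Every tablet after failure taken (the extreme case).** With x tablets taken before failure, reported value = (x + d)/56. Reaching 80% needs 45 tablets, since 0.80 × 56 = 44.8.
- d = 14: 31/56 = 55.4% is reported as 45/56 = 80.4%; 42/56 = 75% is reported as 56/56 = 100%.
- d = 7: 38/56 = 67.9% is reported as 45/56 = 80.4%; reaching 100% needs 49/56 = 87.5%.

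**How many subjects.** At the assumed 96% SVR12, the expected number of non-responders is 36 × 0.04 = 1.44. Only on-treatment failures who stop early are exposed. To be misclassified they must also be poorly adherent and keep dosing after the failing sample.

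**The case against.** The strongest reply is that this is a derivation convention with almost no practical reach. Few subjects, possibly none, will qualify. Confirmation is to be done as soon as possible, so 14 days is a maximum, and the nonresponse criterion is not worded as needing confirmation at all. SAP 4.2.2 rules out inferential statistics for adherence and plans a by-visit accountability listing, where a reader could see the facts. Every affected subject also appears in the discontinued-treatment subgroup of SAP 3.3. All of this stands and limits the importance of the point. It does not correct the derived percentage that feeds the subgroup table and forest plot.

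A reader might infer that a poorly adherent failure will be shown as 100% adherent, or that any true adherence from 55% to 79% is reclassified. The documents do not support either as a general statement. Both need perfect intake for the full 14 days from someone who had missed a quarter or more of the earlier doses (for the 100% case), or nearly half (for the 55% limit).

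The SAP also counts an unreturned bottle as zero tablets taken, which biases adherence downward. That is a separate rule and does not offset this one in any given subject.

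**Conclusion.** The point holds as a minor defect in a stated rule. Adherence can be overstated for subjects who stop early for virologic failure, mainly those first failing at Week 8. With constant adherence the reported value is 1.125 times the true one after 7 further days of dosing and 1.25 times after 14. True values from about 71% and 64% upward then cross the 80% line. The extreme examples (75% read as 100%, 55% read as 80%) hold only with complete intake for 14 days after failure.

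The results rest on two assumptions: a 56-tablet denominator at Day 56, and 7 to 14 days of continued dosing. I place exactly 80% in the upper category, as SAP 4.2.2 does. The primary SVR12 test and its confidence interval do not use adherence and are unaffected. What can change is which SVR12 adherence subgroup an on-treatment failure falls in.

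**What to change.** For these subjects, run numerator and denominator to the same date, and apply the 100% cap afterwards. This changes reporting only.

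The simplest choice is the last dose date. The denominator is tablets prescribed through the last dose (last dose date minus first dose date plus 1, as for exposure in SAP 4.2.1). The numerator is tablets dispensed minus returned from all bottles, with the exclusion of bottles dispensed on or after failure dropped. With constant adherence and 14 further days this gives 70a/70 = a. The extreme cases above become 56/70 = 80% and 45/70 = 64.3%.

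If the sponsor prefers to end at first failure, the numerator must end there too, using the pill count from that visit. That gives 42/56 = 75% for the first extreme case. The two conventions measure different periods and can disagree about the 80% line, so the SAP should name one. Ending at failure also depends on the visit's count being recorded on the CRF. Sites are to make the count, but the documents do not say that tablets sent home again are entered.

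The cost is one SAP sentence and a small programming change. If the SAP is already final, SAP Section 1 provides for documenting the change in the study report.
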